**Table 3-2. Subject Grouping for the CLL Dose Ranging Cohort**

100mg BID N = xx	200mg BID N = xx	400mg BID N = xx	Total N=xx
xx	xx	xx	xx

**Table 3-3. Subject Groupings for the CLL after BCR Targeted Therapy Cohorts**

Non-Richters (Prior BTK Exposure) N = xx	Non-Richters (Prior PI3K Exposure) N = xx	Richters (Prior BTK Exposure) N = xx	Richters (Prior PI3K Exposure) N = xx	Total N = xx
xx	xx	xx	Xx	xx

### 3.3. Strata and Covariates

No planned analyses using strata and/or covariates.

### 3.4. Examination of Subject Subsets

No planned subset analyses.

### 3.5. Multiple Comparisons

Not applicable.

### 3.6. Missing Data and Outliers

#### 3.6.1. Missing Data

In general, missing data will not be imputed unless methods for handling missing data are specified. Exceptions are presented in this document.

The handling of missing or incomplete date for AE onset is described in Section 7.1.5.2, and for prior medication and concomitant medications in Section 7.4.

### 3.6.2. Outliers

Outliers will be identified during the data management and data analysis process, but no sensitivity analyses will be conducted. All data will be included in the data analysis.

### 3.7. Data Handling Conventions and Transformations

The following conventions will be used for the imputation of date of birth when it is partially missing or not collected:

- If only month and year of birth is collected, then “15” will be imputed as the day of birth
- If only year of birth is collected, then “01 July” will be imputed as the day and month of birth
- If year of birth is missing, then date of birth will not be imputed

In general, age (in years) collected at Study Day 1 (the first dosing date of study drug) will be used for analyses and presented in listings. If age at Study Day 1 is not available for a subject, age derived based on date of birth and the Day 1 visit date will be used instead. If an enrolled subject was not dosed with study drug, the enrollment date will be used instead of the Day 1 visit date. For screen failures, the date the first informed consent was signed will be used for the age derivation. Age required for longitudinal and temporal calculations and analyses (eg, estimates of creatinine clearance, age at date of AE) will be based on age derived from date of birth and the date of the measurement or event, unless otherwise specified.

Non-PK laboratory data that are continuous in nature but are less than the lower limit of quantitation (LOQ) or above the upper LOQ will be imputed as follows:

- A value that is 1 unit less than the LOQ will be used to calculate descriptive statistics if the datum is reported in the form of “< x” (where x is considered the LOQ). For example, if the values are reported as < 50 and < 5.0, values of 49 and 4.9, respectively, will be used to calculate summary statistics. An exception to this rule is any value reported as < 1 or < 0.1, etc. For values reported as < 1 or < 0.1, a value of 0.9 or 0.09, respectively, will be used to calculate summary statistics.
- A value that is 1 unit above the LOQ will be used to calculate descriptive statistics if the datum is reported in the form of “> x” (where x is considered the LOQ). Values with decimal points will follow the same logic as above.
- The LOQ will be used to calculate descriptive statistics if the datum is reported in the form of “≤ x” or “≥ x” (where x is considered the LOQ).

Concentration values that are below the limit of quantitation (BLQ) will be presented as “BLQ” in the concentration data listing. Values that are BLQ will be treated as 0 at predose time points, and one half the value of the LOQ at postdose time points for summary purposes. Concentration values that are BLQ will be imputed as one-half LOQ before log transformation.

### **3.8. Analysis Visit Windows**

#### **3.8.1. Definition of Study Day**

Study day will be calculated from the first dosing date of study drug and derived as follows:

- For post-treatment study days: Assessment Date - First Dosing Date + 1
- For days prior to the first dose: Assessment Date - First Dosing Date

Therefore, Study Day 1 is the day of first dose of study drug administration.

Baseline is defined as the last non-missing record on or prior to the date/time of the first dose of study drug, unless otherwise specified.

#### **3.8.2. Analysis Windows**

The nominal visit and related date as recorded on the CRF will be used when data are summarized by visit and no analysis window will be derived. Any data relating to unscheduled visits will not be assigned to a particular visit or time point. In listings, both visit names and dates will be presented.

## **4. SUBJECT DISPOSITION**

### **4.1. Subject Enrollment and Disposition**

A summary of subject enrollment will be provided by the grouping specified in Section 3.2 based on All Enrolled Analysis Set. The summary will present the number and percentage of subjects enrolled. For each column, the denominator for the percentage calculation will be the total number of subjects analyzed for that column.

A summary of subject disposition will be provided based on All Enrolled Analysis Set. This summary will present the number and percentage of subjects in the following categories:

- Treated and Non-treated
- ENTO discontinuations and reasons
- Study discontinuations and reason

The denominator of the percentage calculation will be the total number of subjects in All Enrolled Analysis Set corresponding to that column.

The by-subject listings will be provided by subject identification (ID) number in ascending order to support the above summary tables.

### **4.2. Extent of Study Drug Exposure and Adherence**

Extent of exposure to study drug will be examined by assessing the total duration of exposure to study drug and the level of adherence to the study drug specified in the protocol. The summaries will be based on Safety Analysis Set.

#### **4.2.1. Duration of Exposure to Study Drug**

Total duration of exposure to study drugs will be defined as last dosing date minus first dosing date plus 1, regardless of any temporary interruptions in study drug administration, and will be expressed in months using up to 1 decimal place (eg, 4.5 months). If the last study drug dosing date is missing, the following rules will be followed:

- If the study drug is permanently withdrawn, the latest date among the study drug end date, clinical visit date, laboratory sample collection date, and vital signs assessment date that occurred during the on-treatment period will be used.
- If the study drug completion status is unknown, the earlier of the date of death or database lock date for analysis will be used.

The total duration of exposure to study drug will be summarized using descriptive statistics and using the number and percentage of subjects exposed for at least 1 day, 1, 2, 3, 4, 6, 9, 12 months, and every 6 months thereafter.

The number and percentage of subjects who have dose modification or dose interruption will also be summarized.

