## **2. TYPE OF PLANNED ANALYSIS**

### **2.1. Final Analysis**

After all subjects have completed the study, outstanding data queries have been resolved or adjudicated as unresolvable, and the data have been cleaned and finalized, the final analysis of the data will be performed. Due to the Sponsor's strategic plan, the final CSR will be in synoptic version.

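### With the last dosing date missing and drug completion status unknown, SAP 4.2.1 runs exposure to death or database lock, which overstates it at a final analysis

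*SAP*

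**What the plan says.** SAP 4.2.1 defines the quantity as follows: "Total duration of exposure to study drugs will be defined as last dosing date minus first dosing date plus 1, regardless of any temporary interruptions". Imputation has a precondition: "If the last study drug dosing date is missing, the following rules will be followed". Two cases follow.

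- Drug known to be permanently withdrawn: the SAP takes "the latest date among the study drug end date, clinical visit date, laboratory sample collection date, and vital signs assessment date", restricted to the on-treatment period.
- Completion status not known: "If the study drug completion status is unknown, the earlier of the date of death or database lock date for analysis will be used".

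Duration is then summarised with descriptive statistics and as the "number and percentage of subjects exposed for at least 1 day, 1, 2, 3, 4, 6, 9, 12 months, and every 6 months thereafter".

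SAP 2.1 is the only analysis listed under planned analyses. It takes place "After all subjects have completed the study, outstanding data queries have been resolved or adjudicated as unresolvable" and the data have been cleaned.

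**The concern.** Using the lock date as a stand-in for the last dose makes sense for a subject who is still taking drug when the data are cut. At an analysis run after everyone has completed the study, no such subject should exist. Someone with no last dosing date and no known completion status is then unaccounted for. Study drug is dispensed at the Day 1 visit of each 28-day cycle (Protocol 6.3.1), so dosing is unlikely to continue long after the last visit. The rule still counts that person as exposed until lock, or until a recorded death.

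At stake is the accuracy of the exposure table: the mean, the maximum, and the proportions reaching the longer duration categories. These describe how long the drug was taken and give context to the safety data.

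**Working it through.** The plan gives no figure for this point, so there is none to reproduce. The check applies the SAP's own formula to dates in the documents.

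**Inputs**
- Formula (SAP 4.2.1): last dosing date − first dosing date + 1.
- Latest possible first dose for the first 109 subjects: 14 March 2014, the date of the Investigator's Brochure edition behind the N=109 table (Protocol 1.7.1, Table 1-1).
- Earliest possible lock: 31 March 2017. The SAP is based on Amendment 8 of that date and is to be finalised before the database is (SAP 1). The actual lock date is not given.
- Cohort size: up to 40 for CLL, FL, DLBCL and MCL (Protocol 8.7).
- Assumption: one month = 365.25/12 = 30.4375 days. The SAP does not define the conversion.
- Assumption: one affected subject, no recorded death, last seen at Day 56. Days 28 and 112 are shown as a range.

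**Imputed exposure under the current rule**
14 March 2014 to 31 March 2017 is 1,113 days; 1,113 + 1 = 1,114 days. 1,114 / 30.4375 = 36.6 months. This is a floor, because an earlier first dose or a later lock only lengthens it. Assumed locks of 31 March 2018 and 31 March 2019 give 1,479 days (48.6 months) and 1,844 days (60.6 months).

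**Excess over the time to last contact (earliest lock)**

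| Last seen | Months to last contact | Excess, months | Shift in mean, n = 40 |
|---|---|---|---|
| Day 28 | 0.9 | (1,114 − 28)/30.4375 = 35.7 | 35.7/40 = 0.89 |
| Day 56 | 1.8 | (1,114 − 56)/30.4375 = 34.8 | 34.8/40 = 0.87 |
| Day 112 | 3.7 | (1,114 − 112)/30.4375 = 32.9 | 32.9/40 = 0.82 |

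For Day 56 with the two later assumed locks, the excess is 46.8 and 58.7 months, and the shift in the mean is 1.17 and 1.47 months.

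**Duration categories**
At 36.6 months the subject counts in every category up to at least 36 months. Time to last contact at Day 56 (1.8 months) supports only the 1-day and 1-month categories. Each category from 2 to 36 months is therefore raised by 1/40 = 2.5 percentage points.

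**What cannot be computed**
The documents do not say how many subjects meet both conditions. They give no enrolment dates for the cohorts added later, so no comparable floor can be set for those.

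**The case against.** The strongest reply is that the rule may apply to almost nobody. It needs a missing last dosing date and also an unknown completion status. A reader might infer that every subject lost to follow-up is affected; the documents do not support that. The SAP tabulates drug discontinuations with reasons (SAP 4.1), and the source data are to include medication end dates and the reason for early discontinuation (Protocol 9.1.5). Queries are to be closed or declared unresolvable before the final analysis. A lost subject recorded as off drug falls under the withdrawn-drug rule. This stands, and it is why the number affected is probably small.

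Second, Protocol 8.10 allows final reporting 48 weeks after the last accrual if that comes before all subjects have completed, and Protocol 5.6 allows treatment to continue indefinitely. SAP 7.2 also mentions subjects ongoing at an interim analysis. Some subjects could then be on drug at lock, and for them the lock date is sensible. This stands in part. It is a reason to keep the lock date for subjects confirmed on drug. It does not justify applying that date to subjects whose status is unknown, and SAP 2.1 itself has all subjects complete first.

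Third, a reader might infer that late adverse events and laboratory values would be labelled treatment-emergent. The documents do not show this. SAP 4.2.1 sets the imputation for exposure duration only, the windows in SAP 7.1.5 and 7.2 do not cite it, and a lost subject has few late data to mislabel.

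Fourth, the medians and quartiles would barely move with one subject in 40, and the by-subject listings of administration and accountability (SAP 4.2.2) could reveal an implausible duration. Both are fair, but neither corrects the mean or the category percentages.

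**Conclusion.** The point holds as a minor error in a stated rule. For a subject with a missing last dosing date, unknown completion status and no recorded death, exposure is extended to lock with no limit at last contact. For one of the first 109 subjects that means at least 36.6 months. If last seen at Day 56, the excess is at least about 35 months, with about 0.9 months added to the mean of a 40-subject cohort and 2.5 points added to each category from 2 to 36 months. A recorded death shortens the imputed period, but the rule still counts the whole interval from last contact to death as exposure.

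These sizes rest on a single hypothetical subject, the 14 March 2014 and 31 March 2017 bounds, and a 30.4375-day month. A reader might count from the end of December 2013, the month in which initial CLL results were presented, and arrive at 39 months. That is not a safe floor: the documents give no individual first-dose or loss dates, and the figure does not deduct time actually on study.

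The effect is confined to the descriptive exposure summary. The primary endpoint, the PFS rate, has its own event and censoring rules (SAP 6.1.1 and Appendix 2) and is unaffected.

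**What to change.** Replace the second rule in SAP 4.2.1 with two sentences. (1) If the last dosing date is missing and completion status is unknown, use the latest recorded study drug, clinic visit, laboratory or vital-signs date, no later than the date of death. (2) Use the database lock date only for subjects confirmed to be still on study drug at lock, if there are any.

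The first sentence should not carry over the on-treatment restriction from the withdrawn-drug rule, because the end of treatment is what is unknown for these subjects.

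The cost is two sentences in the SAP before database finalization and a small change to one derivation. The dates needed are already collected.

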#### **4.2.2. Adherence to Study Drug**

By-subject listings of ENTO administration, accountability (dispenses and returns), and dose interruption/modification will be provided by subject ID number (in ascending order) and visit (in chronological order).

#### **4.3. Protocol Deviations**

Subjects who do not meet the eligibility criteria for study entry but are enrolled in the study will be summarized regardless of whether they are exempted by the sponsor or not. The summary will present the number and percentage of subjects who do not meet at least 1 eligibility criterion and the number of subjects who do not meet specific criteria based on the All Enrolled Analysis Set. A by-subject listing will be provided for those subjects who do not meet at least 1 eligibility (inclusion or exclusion) criterion. The listing will present the eligibility criterion (or criteria if more than 1 deviation) that subjects do not meet and related comments, if collected.

Protocol deviations occurring after subjects enter the study are documented during routine monitoring. The number and percentage of subjects with important protocol deviations by deviation reason (eg, nonadherence to study drug, violation of select inclusion/exclusion criteria) will be summarized for the All Enrolled Analysis Set. A by-subject listing will be provided for those subjects with important protocol deviation.

## **5. BASELINE CHARACTERISTICS**

### **5.1. Demographics**

Subject demographic variables (ie, age, sex, race, and ethnicity) and baseline characteristics (body weight [in kg], height [in cm], body mass index [BMI; in kg/m^2]) will be summarized using descriptive statistics for continuous variables and using number and percentage of subjects for categorical variables. The summary of demographic data will be provided for the FAS.

A by-subject demographic listing, including the informed consent date, will be provided by subject ID number in ascending order.

### **5.2. Other Baseline Characteristics**

Other baseline characteristics include Karnofsky performance status and creatinine clearance (mL/min). These baseline characteristics will be summarized using descriptive statistics for continuous variables and using number and percentage of subjects for categorical variables. The summary of these baseline characteristics will be provided for the FAS. No formal statistical testing is planned.

A by-subject listing of other baseline characteristics will be provided by subject ID number in ascending order.

### **5.3. Medical History**

Medical history will be collected at screening for the disease-specific and general conditions (ie, conditions not specific to the disease being studied).

Disease-specific medical history will be summarized by the number and percentage of subjects with each prepopulated condition. The summary will be provided for the FAS. No formal statistical testing is planned. Time since diagnosis (years) will be calculated by  $(\text{date of the first dosing date of study drug} - \text{date of diagnosis})/365.25$ . Time since diagnosis will be summarized using summary statistics for a continuous variable. Disease stage at diagnosis and at screening will be summarized using summary statistics for a categorical variable. No formal statistical testing is planned. A by-subject listing of disease-specific medical history will be provided by subject ID number in ascending order.

In deriving the time since diagnosis, all partial dates of diagnosis and last regimen will be identified, and the partial dates will be imputed as follows:

- If day and month are missing but year is available, then the imputed day and month will be 01 Jan.
- If day is missing but the month and year are available, then the imputed day will be the first day of the month.
- Partial date will not be imputed if the year is missing.

General medical history data will not be coded but will be listed only. A by-subject listing of general medical history will be provided by subject ID number in ascending order.

#### **5.4. Prior Anticancer Therapy**

Number of prior regimens and time since the completion of the last regimen will be summarized using descriptive statistics based on the FAS. A partial completion date will be imputed using the algorithm defined in Section 5.3.

For the cohorts of CLL after BCR Targeted Therapy, prior BCR therapy, time since treatment failure, treatment failure reason, and best clinical response will be summarized.

A by-subject listing of prior anticancer therapy will be provided by subject ID number in ascending order.

## **6. EFFICACY ANALYSES**

### **6.1. Primary Efficacy Endpoint**

#### **6.1.1. Definition of the Primary Efficacy Endpoint**

The primary efficacy endpoint of this study is PFS rate at 16 weeks (CLL after BCR targeted therapy, MCL, and DLBCL) or 24 weeks (CLL and iNHL). PFS is defined as the interval from the first dose of ENTO to the earlier of the first documentation of definitive disease progression or death from any cause.

The determination of NHL response and progression (defined in the Protocol Section 6.20) is based on standardized criteria {Cheson 2007, Rourke 2010} as specifically modified for this study to reflect the biology of the diseases under study and the pharmacology of ENTO and the methods to be used in evaluation. The determination of CLL response and progression (defined in the Protocol Section 6.21) is based on standardized IWCLL criteria {Hallek 2008} as specifically modified for this study considering the pharmacology of ENTO and the methods to be used in evaluation.

In accordance with the Gilead Protocol 339-0102 Imaging Charter, if there is uncertainty regarding whether there is true progression, the subject may continue study treatment and remain under close observation (eg, evaluated at 4-week intervals). If subsequent evaluations suggest that the subject is experiencing progression, then the date of progression should be the time point at which progression was first identified. A single PD determination followed by a determination that indicated either no change or improvement in disease prior to the single PD observation will not be considered as PD.

Subjects without progression or death will be censored at the last adequate post-baseline tumor assessment time. If subjects receive other anti-cancer therapy or have  $\geq 2$  consecutive missing post-baseline tumor assessments immediately before documented progression or death, they will be censored at the last adequate post-baseline tumor assessment time before starting anti-cancer therapy or before  $\geq 2$  consecutive missing tumor assessments whichever is earlier. If subjects don't have adequate baseline tumor assessment or adequate post-baseline tumor assessment, they will be censored on the date of Study Day 1 unless subjects die before or on the 2nd scheduled post-baseline tumor assessment without receiving other anti-cancer therapy. Please see [Appendix 2](#) for details on PFS event and censoring time derivation.

The findings of the IRC will be considered primary for analyses of PFS rate. The findings of investigator assessment will be provided in the listing.

